5.2 Secondary endpoints

Participation rate to the breast cancer screening programme will be assessed as a percentage of women who participate, both in intervention and in the control group. The statistical hypothesis for the secondary endpoint is of non-inferiority. This hypothesis will be considered only if the null hypothesis related to the primary endpoint will be rejected.

Satisfaction with the information given (intervention and control group) will be measured using 8 items regarding length, quantity, clarity, balance, helpfulness in making decision and women willingness to recommend it to other women with three points scale.

The time spent on the pages in the web decision aid and in the web brochure will be assessed through Pickwick software. Only for the web decision aid, through the same software, the number of pages visited, the frequency of access and level of detail reached will be calculated.

Use of/experience with other screenings will be measured using one item on the participating in other screenings programme.

Decisional conflict will be assessed using the validated and widely used Decisional Conflict Scale-SURE version (28). This four-item scale will assess the women's knowledge of the options available, the clarity about the benefits and risks most important for them, sufficient level of support and being sure about the best choice. Since no Italian translation of this scale is available, the scale will be translated for this study.

The perceived risk of breast cancer will be assessed using one item with a five verbal response categories ranging from "much lower" to "much higher" than the average.

Internet use will be measured using one item regarding the frequency of the Internet use for health information.

5.3 Translation of items

The items have been translated in Italian through a multistep process employing a standardized methodology. Briefly, one professional translator and two members of coordinating center (IRCCS Istituto Mario Negri) produced three independent Italian translations. After discussion, a common Italian version was produced. This version has been evaluated by partners (epidemiologists with experience in breast cancer screening, experts in communication, researchers of the project) in terms of use of simple, and correct language.

The preliminary Italian version of the questionnaires has been tested in a small group of women in order to evaluate clarity, understandability and length.

At the end of this process a final version has been established (Appendix 3).

6. PATIENT SELECTION CRITERIA

6.1 Study participants

All the women eligible to receive an invitation letter to be screened will be contacted to enter the trial.

6.2 Inclusion criteria

- Women aged 45-69, according to the target age of the screening centres involved;
- New invited women in mammography screening programme.

6.3 Exclusion criteria

- None.

7. STUDY ASSESSMENTS

After registering in the web platform and signing the informed consent, participants must fill in a baseline questionnaire for participation in the study.

At baseline questionnaire, the following parameters will be evaluated:

- ✓ Demographics
- ✓ Use of internet
- ✓ Previous mammography test
- ✓ Previous participation at screening programmes
- ✓ Family history of breast cancer
- ✓ Perceived risk of breast cancer
- ✓ Knowledge on the breast cancer screening
- ✓ Attitude on the breast cancer screening
- ✓ Intention on the breast cancer screening

Baseline questionnaire will be performed prior to the randomization.

Follow-up questionnaire will be performed 7-10 days after randomization, before the appointment at the breast cancer screening.

At follow-up questionnaire, the following parameters will be evaluated:

- ✓ Knowledge on the breast cancer screening
- ✓ Attitude on the breast cancer screening
- ✓ Intention on the breast cancer screening
- ✓ Satisfaction and acceptability of the information received (web decision aid and web brochure)
- ✓ Decisional conflict

See Appendix 3 for both the baseline and the follow-up questionnaires.

8. WOMEN AND STUDY WITHDRAWAL

8.1 Women withdrawal

The women have the right to voluntarily withdraw from the study at any time for any reason.

Reasons for withdrawal from the study may include, but are not limited to, the following:

- Women withdrawal of consent at any time
- Loss to follow-up.

9. STATISTICAL CONSIDERATION AND ANALYTICAL PLAN

9.1 Definition of study populations

9.1.1 All Participants Analysis Set

The All Participants Analysis Set is defined as all women who provided informed consent, were enrolled in the study and filled the baseline questionnaire. The listings of all variables will be based on the All Participants Analysis Set.

9.1.2 Intent-to-Treat (ITT) Analysis Set

The ITT analysis set is defined as all randomized women that respond to the follow-up questionnaire. Women will be analyzed according to the randomization arm.

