4.2 Randomization

A central system for randomization will be used inside the web platform. The women will be randomized after they register to the platform, sign the informed consent and fill-in the baseline questionnaire. The random allocation will be on a 1:1 ratio basis.

The overall duration of the study is 15 months: 14 months for invitation of the women and maximum 1 months of follow-up.

The study outline is illustrated in Figure 1.

Figure 1 Study flow-chart

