9.1.3 Sample size

The primary analysis will compare the proportion of women who make an informed choice, using the chi-squared test in the two study groups. Based on the previous studies (21, 22) we judge an absolute difference of 10% as the minimum important difference for the sample size calculation. Assuming that one of the group proportions is 50%, in order to achieve 80% power to detect a group difference with a two-sided significance level of 5%, we require 816 women at follow-up. Allowing for an estimated response rate of 15% and early drop-out of one-third of initial participants, we will invite 8160 women to take part in the study.

If the null hypothesis related to the primary endpoint will be rejected, the first of the secondary endpoints will be analysed. The power of the analysis for this non-inferiority test - with one-sided tail - will be considered according with the participation rate at breast cancer screening, as reported in the table below.

Participation rate at breast cancer screening (control group)	Participation rate at breast cancer screening (intervention group)	Δ	Number of patients for each arm	Power (1-β)
40%	35%	5%	408	0.29122
40%	30%	10%	408	0.82777
40%	25%	15%	408	0.99289
40%	20%	20%	408	0.99996

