9.2 Statistical analysis

We will conduct a descriptive analyses to describe the study participants. Possible baseline differences between trial arms will be statistically tested.

For primary endpoint statistical analysis will be performed on an intention to treat approach: all the randomised women compliant to follow-up will be included in the analysis in the groups assigned at the randomization. The impact of the web decision aid on the primary endpoint will be analysed using Chi-square test.

For secondary endpoints we will use Chi-square test to analyse binary endpoints and 2-sided t-test for continuous endpoints, with a significance level of 5%.

We will use SAS statistical software, version 9.2.

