12.6 Study timetable and end of study

The end of the study is defined as ‘the last follow-up questionnaire of the last participant undergoing the study’.

The study is expected to start in September 2017 and to end in December 2018.

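### The ITT set is a complete-case set of questionnaire responders with no missing-data analysis, and the population and data source for screening participation are not stated

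*Combined protocol and SAP*

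**What the plan says.** Section 9.1.2 defines the main comparative set: "The ITT analysis set is defined as all randomized women that respond to the follow-up questionnaire". Section 9.2 repeats this for the primary endpoint under the heading of intention to treat: "all the randomised women compliant to follow-up will be included in the analysis". Women are kept in the arm to which they were assigned.

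The only other set, in Section 9.1.1, is wider but has one stated use: "The listings of all variables will be based on the All Participants Analysis Set". Loss of participants appears only as an inflation factor in Section 9.1.3, "early drop-out of one-third of initial participants". The available text describes no imputation, sensitivity analysis or comparison of response by arm.

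On screening participation, Section 5.2 says: "Participation rate to the breast cancer screening programme will be assessed as a percentage of women who participate". It gives no denominator, data source or time window. Section 9.2 names no analysis set for secondary endpoints, and the participation power table in Section 9.1.3 uses 408 per arm. On timing, Section 7 says: "Follow-up questionnaire will be performed 7-10 days after randomization, before the appointment at the breast cancer screening". Section 12.6 ends the study at "the last follow-up questionnaire of the last participant undergoing the study".

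**The concern.** An intention-to-treat analysis keeps women in their assigned arm and includes all who were randomised. The plan keeps the first property and drops the second. Whether a woman returns the follow-up questionnaire is known only after she has been given either a multilevel decision aid of 16–20 screens or a brochure. Response could therefore differ by arm and be related to being informed. Randomisation does not protect a comparison restricted in this way, and nothing planned would show whether the result depends on the women left out.

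Participation raises a separate problem. Attendance at mammography can in principle be known for every randomised woman, so there is no reason to condition it on the questionnaire. Yet responders form the only comparative set defined, and the 408 per arm equals 816/2. That participation is restricted to responders is an inference from these two facts; the plan does not say so. A non-inferiority conclusion drawn from responders alone could miss lower attendance among non-responders. The source is also open for responders themselves, because the questionnaire comes before the appointment and the study ends at the last questionnaire.

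**Working it through.** **Inputs from the plan.** 8160 invited, 15% response, one-third early drop-out, 816 at follow-up, 50% in one group, a 10-point difference, two-sided 5%, 80% power (Section 9.1.3); 1:1 allocation (Section 4.2); 40% control participation and 408 per arm (power table, Section 9.1.3).

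**Reproducing the plan.** The continuity-corrected two-proportion formula for 50% v 60% gives 408 per arm, so 816 in total (388 per arm without the correction). 8160 × 0.15 = 1224, and 1224 × 2/3 = 816. The sample size reproduces, and 816 is the number of responders.

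**How many randomised women are left out.** Section 4.2 says: "The women will be randomized after they register to the platform, sign the informed consent and fill-in the baseline questionnaire". Some of the drop-out may therefore precede randomisation. If a share f of the 408 lost drop out afterwards, the number randomised is 816 + 408f.

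| f | Randomised | Per arm | Left out |
|---|---|---|---|
| 0 | 816 | 408 | 0% |
| 0.5 | 1020 | 510 | 204 (20%) |
| 1 | 1224 | 612 | 408 (33%) |

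**Primary endpoint, non-responder = not informed.** Assume 60% v 50% informed among responders and equal loss by arm (pooled two-proportion test).
- Responders only, 408 per arm: 60% v 50%, p = 0.004.
- 20% loss: 0.6 × 408/510 = 48.0% and 0.5 × 408/510 = 40.0%; z = 2.57, p = 0.010.
- 33% loss: 0.6 × 408/612 = 40.0% and 0.5 × 408/612 = 33.3%; z = 2.42, p = 0.016.

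**Unequal response under the same rule.** Let intervention response be g below control, with the mean response fixed. At mean response 2/3 and 612 per arm, compare 0.6 × (2/3 − g/2) with 0.5 × (2/3 + g/2).
- z = 1.96 at g = 0.023, a gap of 2.3 points.
- The difference is zero when 0.4 − 0.3g = 0.333 + 0.25g, which gives g = 0.0667/0.55 = 0.121, a gap of 12.1 points.
- At mean response 0.8 and 510 per arm, z = 1.96 at g = 0.035, a gap of 3.5 points.

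**Bias in the responder analysis itself (assumed retention).** Suppose there is no true effect and 50% are informed in both arms. In the intervention arm 70% of informed and 50% of uninformed women respond; control loss is unrelated to outcome. Responders then show 0.35/(0.35 + 0.25) = 58.3% v 50%, a spurious 8.3 points. With 408 per arm, a bias of that size favours the decision aid in about 67% of trials. A 5-point bias does so in about 30% and a 2-point bias in about 8%, against a nominal 2.5% in that direction.

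**Participation.** If attendance is equal among responders and loss is equal by arm, the overall fall is the loss share times the fall among non-responders. A 5-point overall fall is hidden if non-responders differ by 5/(1/3) = 15 points at 33% loss, or 5/0.2 = 25 points at 20% loss.

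Non-inferiority power is Φ(d/√(2 × 0.4 × 0.6/n) − 1.96). This assumes 40% in both arms, the table's difference d as margin, and one-sided 2.5%; the plan says only one-sided.

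| n per arm | 5 points | 10 points |
|---|---|---|
| 408 | 0.308 (plan 0.29122) | 0.830 (plan 0.82777) |
| 510 | 0.371 | 0.903 |
| 612 | 0.431 | 0.946 |

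The formula is within 0.02 of the plan's figures at 408. One-sided 5% gives 0.426 and 0.898 and does not match.

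**The case against.** Informed choice cannot be observed in a woman who does not answer, and the plan discloses openly whom it analyses. If all the drop-out precedes randomisation, responders and randomised women coincide and nothing changes. With equal loss of 20% or 33% the primary result stays significant even when non-responders count as not informed. The 2.3-point tipping gap needs that strict rule plus unequal response, and the documents give no response rates by arm.

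On participation, Section 9.2 ties the responder set to the primary endpoint only, and 408 per arm may be no more than a conservative input to a power table. The screening centres issue the study invitations (Section 4), users are entered from centre lists (Section 10.3), and centre investigators have data-entry credentials (Section 10.2). Attendance might therefore reach the trial through the centres. Figure 1 is not available to show whether it includes such a step.

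Much of this stands as a limit on size. The loss is a range, the scenarios are assumptions, and the responder restriction for participation is an inference. It does not rescue the label or supply the missing analyses. The plan does not place the drop-out before randomisation, and Section 8.1 lists loss to follow-up among the reasons for withdrawal. Testing baseline differences between arms (Section 9.2) is not a missing-data analysis. None of the provisions on centres and user IDs names attendance records.

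**Conclusion.** The concern holds. As written, the set called ITT does not include all randomised women, and no analysis tests whether the primary result depends on those left out. On the plan's own rates the excluded share lies between 0 and one-third of those randomised. The sample-size arithmetic is correct; the fault lies in the analysis set. Whether the conclusion would change depends on assumptions: it survives equal loss under the strictest rule used here, but a response gap of about 2 to 4 points between arms is enough to remove significance under that rule.

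For participation, the population, data source and counting date are not stated in the available text. A restriction to responders is the likely reading, though not a certain one. It would leave out women whose attendance need not depend on the questionnaire and give up power: at 10 points, 0.83 against up to 0.95. Because participation is tested only if the primary null hypothesis is rejected, bias in the primary comparison also affects whether that test is made.

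**What to change.** 1. Define ITT as all randomised women, analysed as assigned, and label the responder analysis complete-case.
2. Keep the complete-case comparison for informed choice and report response by arm. Add two sensitivity analyses in all randomised women: multiple imputation by arm from baseline knowledge, attitude, intention and education, plus the end-of-session intention item (Section 5.1) where recorded; and non-responder = not informed.
3. Make all randomised women the primary population for participation, with attendance linked by study ID whether or not the questionnaire was returned. State the data source and the date by which attendance is counted, and check the end-of-study definition in Section 12.6 against that date.

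The cost is mainly SAP wording and extra analysis, since the baseline predictors are already collected before randomisation. Attendance status is needed for up to about 408 more women. A linkage procedure must be written, but the endpoint needs a defined attendance source in any case. The resulting estimates may be less favourable to the decision aid.

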9.1.3 Sample size

The primary analysis will compare the proportion of women who make an informed choice, using the chi-squared test in the two study groups. Based on the previous studies (21, 22) we judge an absolute difference of 10% as the minimum important difference for the sample size calculation. Assuming that one of the group proportions is 50%, in order to achieve 80% power to detect a group difference with a two-sided significance level of 5%, we require 816 women at follow-up. Allowing for an estimated response rate of 15% and early drop-out of one-third of initial participants, we will invite 8160 women to take part in the study.

If the null hypothesis related to the primary endpoint will be rejected, the first of the secondary endpoints will be analysed. The power of the analysis for this non-inferiority test - with one-sided tail - will be considered according with the participation rate at breast cancer screening, as reported in the table below.

Participation rate at breast cancer screening (control group)	Participation rate at breast cancer screening (intervention group)	Δ	Number of patients for each arm	Power (1-β)
40%	35%	5%	408	0.29122
40%	30%	10%	408	0.82777
40%	25%	15%	408	0.99289
40%	20%	20%	408	0.99996

9.2 Statistical analysis

We will conduct a descriptive analyses to describe the study participants. Possible baseline differences between trial arms will be statistically tested.

For primary endpoint statistical analysis will be performed on an intention to treat approach: all the randomised women compliant to follow-up will be included in the analysis in the groups assigned at the randomization. The impact of the web decision aid on the primary endpoint will be analysed using Chi-square test.

For secondary endpoints we will use Chi-square test to analyse binary endpoints and 2-sided t-test for continuous endpoints, with a significance level of 5%.

We will use SAS statistical software, version 9.2.

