5.1 Primary endpoints

Informed choice will be measured according to the three-dimensional framework of Marteau et al. (26), which covers knowledge, attitude and intention. The statistical hypothesis for the primary

endpoint is of superiority, the study is designed to detect a 10% difference between the control and the intervention group, according to the literature available (22, 27).

Knowledge will be measured using a questionnaire developed on the basis of literature (22, 27). It will be structured in thirteen questions with multiple choice answers, with two to three options. Ten questions will be qualitative and 3 will be numerical. The score and threshold to reach an “adequate knowledge” were decided *a priori*, following the approach described in the literature (22, 27). Each correct answer will receive one point. The maximum total score is 13 out of 13. A score of 8 out of 13 (about 60%) or higher would be considered “adequate knowledge”.

Attitude will be measured through a scale used in the literature available (22, 27), consisting of six items with five response options from 1 to 5, with a total score from 6 to 30. For informed choice, we set the threshold for a positive attitude at 24 and consequently the score <24 point a negative attitude.

Intention to be screened will be measured using one item with five responses: Definitely will, Likely to, Unsure, Not likely to, Definitely will not. For informed choice, we classified “definitely will” and “likely to” as positive intentions. This item will be collected at the end of the information session on the web and in the follow-up questionnaire. In case of no consistency between the two answers, the answer in the follow-up questionnaire will be considered as conclusive.

The informed choice will be assessed as a dichotomous outcome. A woman will be considered as able to express an informed choice if she has adequate knowledge and her attitudes and intentions are consistent (both positive or both negative) in the follow-up questionnaire.

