14.3 Appendix 3: baseline and follow-up questionnaires

BASELINE QUESTIONNAIRE

SOCIODEMOGRAFIC

Nationality:

- a) Italian
- b) Other, please specify _____

Education

- Elementary
- Lower middle
- Higher middle
- Degree
- Other

Marital status

- Single
- Married or living together
- Separated or divorced
- Widowed

Employment status

- Paid work (full or part time)
- No paid work (retired, housewife, other)

Do you use internet to search for health information?

- Never
- A few times a month
- At least once a week

- Several times a week
- Daily

Have you already had a mammography?

- Yes, in a public facility, when? _____(year)
- Yes, in a private facility, when? _____(year)
- No

Has anyone in your family or your friends had breast cancer?

- Yes
- No

Have you ever had a tumor?

- Yes If Yes, type of tumor _____
- No

Have you participated in other organized screening programs?

Fecal occult blood tests for colorectal cancer	 Yes  No
Pap test for cervical cancer	 Yes  No

PERCEIVED RISK

Perceived risk of breast cancer relative to the average woman

Much lower	A bit lower	About the same	A bit higher	Much higher
------------	-------------	----------------	--------------	-------------

KNOWLEDGE

What is a SCREENING mammogram?

- A mammogram you have when you're healthy
- A mammogram you have if you notice a change or lump in your breast

An organized mammography screening program can detect a breast cancer in an early stage and lead to less invasive surgery and treatment

True

False

Which of the following statements about mammography reflects your opinion?

Regular mammography every two years in women who are well:

Prevents the risk of breast cancer

Does not prevent the risk of breast cancer

Who do you think is more likely to die from breast cancer?

Women who have screening mammograms

Women who do not have screening mammograms

Do you think a screening mammogram will find every breast cancer?

Yes

No

Do all women with an abnormal screening mammogram result have breast cancer?

Yes

No

Which of these 2 statements best describes over-detection?

Screening finds a cancer that would never have caused trouble

Screening finds an abnormality but extra tests show it is not cancer

Screening leads some women with a harmless cancer to get treatment they do not need.

True

False

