In the organized mammography screening program, the presence of two expert radiologists increases the ability to identify a breast tumor

- True
- False

The usefulness of an organized mammography screening program is:

- Totally recognized by doctors and researchers
- Questioned by some doctors and researchers

For the next few questions, I would like you to imagine 1000 ordinary women who are 50 years old who have participated regularly in organized mammography screening program for 30 years

How many women do you think will avoid dying from breast cancer because of screening?

- 8
- 50
- 150

How many women do you think will be diagnosed and treated for a breast cancer that is not harmful?

- 4
- 25
- 70

Now, I would like you to imagine 1000 ordinary women who are 50 years old who have not participated in organized mammography screening program, in their next 30 years.... How many die of breast cancer?

- 20
- 80
- 140

ATTITUDE

For you, having breast screening is.....

A bad thing	Not a bad thing
1 2 3 4 5	
Beneficial	Not beneficial
1 2 3 4 5	
Harmful	Not harmful
1 2 3 4 5	
A good thing	Not a good thing
1 2 3 4 5	
Worthwhile	Not worthwhile
1 2 3 4 5	
Important	Unimportant
1 2 3 4 5	

INTENTION

Intending to be screened

Definitely will	Likely to	Unsure	Not likely to	Definitely will not
-----------------	-----------	--------	---------------	---------------------

FOLLOW-UP QUESTIONNAIRE

ATTITUDE

For you, having breast screening is.....

A bad thing

Not a bad thing

1 2 3 4 5

Beneficial

Not beneficial

1 2 3 4 5

Harmful

Not harmful

1 2 3 4 5

A good thing

Not a good thing

1 2 3 4 5

Worthwhile

Not worthwhile

1 2 3 4 5

Important

Unimportant

1 2 3 4 5

SATISFACTION/ACCEPTABILITY OF THE INFORMATION

Thinking back to the type of information material you have read ...			
Was there enough information?	Too much	Too little	Fair
Was the information on benefit new to you?	All or almost all	Some	None
Was the information on harm new to	All or almost all	Some	None

you?			
Was the information clear?	All or almost all	Some	None
The information seemed...	In favor of screening	Balanced	Against screening
Did it help you to decide?	Yes	Not much	No
Would you recommend it to other women?	Yes	Not much	No
Only for Decision-Aid	All or almost all	Some	None
Was the controversy new to you?			

DECISIONAL CONFLICT (SURE QUESTIONNAIRE)

Sure of myself

Do you feel SURE about the best choice for you?

Yes
 No

Understanding information

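### The primary analysis is a valid but unadjusted chi-square, although all three components of informed choice are measured before randomisation: a modest, avoidable loss of precision

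*Combined protocol and SAP*

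**What the plan says.** Two places set the primary test, and they agree. Section 9.1.3: "The primary analysis will compare the proportion of women who make an informed choice, using the chi-squared test in the two study groups". Section 9.2: "The impact of the web decision aid on the primary endpoint will be analysed using Chi-square test". Neither names a covariate, and no adjusted primary, supporting or sensitivity model appears elsewhere.

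Section 5.1 defines informed choice as a yes/no outcome, met by a woman "if she has adequate knowledge and her attitudes and intentions are consistent (both positive or both negative) in the follow-up questionnaire".

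The same three components are measured before allocation. Section 4.2: "The women will be randomized after they register to the platform, sign the informed consent and fill-in the baseline questionnaire". Section 7 makes the questionnaire a condition of entry ("participants must fill in a baseline questionnaire for participation in the study") and fixes its timing: "Baseline questionnaire will be performed prior to the randomization". It lists knowledge, attitude and intention under both the baseline and the follow-up questionnaire. Appendix 3 prints the same items in both: 13 knowledge questions (one is "Do you think a screening mammogram will find every breast cancer"), the six-item attitude scale introduced by "For you, having breast screening is", and one intention item.

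The only uses of baseline data in section 9.2 are description of participants and significance tests between arms.

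**The concern.** When the components of an endpoint are also measured before randomisation, they are natural prognostic covariates. Adjusting for them removes outcome variation that has nothing to do with the arm. The result is a narrower confidence interval and somewhat more power from the same women, and chance imbalance in those components is taken into account.

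Three features of this trial make that worth having:

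- Evaluable women are costly to obtain: 8160 invitations for 816, or ten per woman.
- The power reserve is small (see the working).
- The non-inferiority hypothesis on screening participation is considered only if the primary null hypothesis is rejected (sections 5.2 and 9.1.3), so power on the primary test carries forward.

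Section 9.2 also plans baseline significance tests without saying what follows from them. A prespecified covariate set leaves no room for deciding on adjustment after those tests have been seen.

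**Working it through.** **1. The plan's own figure.** Inputs from section 9.1.3: 50% in one group, a 10-point difference (so 60% in the other), 80% power, two-sided 5%.

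- Uncorrected: n = [1.96·√(2·0.55·0.45) + 0.8416·√(0.50·0.50 + 0.60·0.40)]² / 0.10² = 387.3 per arm.
- With continuity correction: n/4·[1 + √(1 + 4/(n·0.10))]² = 407.1, rounded up to 408 per arm, or 816. This matches.
- Invitations: 816 / (0.15 × 2/3) = 8160. This matches.

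**2. Unadjusted precision at 408 per arm.** SE = √(0.49/408) = 0.03466, where 0.49 = 0.25 + 0.24.

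- 95% CI half-width = 1.96 × 0.03466 = 6.79 points.
- Power = Φ(0.10/0.03466 − 1.96) = Φ(0.926) = 82.3%. The pooled-variance formula gives 82.0%, and 80.1% with the continuity correction that reproduces 816.

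**3. Effect of adjustment.** If the baseline covariates explain a share R² of outcome variance, the variance of the risk difference is multiplied by (1 − R²). Hence:

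- power = Φ(0.10/√(0.49/408·(1 − R²)) − 1.96)
- equivalent sample = 816/(1 − R²)
- half-width = 1.96·√(0.49/408·(1 − R²))

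The documents do not give R². It was obtained by simulating the composite (knowledge above its cut-off, and attitude and intention of the same sign). All of these inputs are assumptions: 55% informed choice overall, 60–80% positive attitude, 85–90% positive intention, attitude–intention correlation 0.5–0.7, and a baseline-to-follow-up correlation r for each component. There were 12 settings per value of r and 400,000 women per setting. The covariates were baseline knowledge, attitude and five-level intention only.

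| r (assumed) | R² | Formula power | Equivalent sample | Half-width (points) |
|---|---|---|---|---|
| 0 | 0% | 82.3% | 816 | 6.79 |
| 0.3 | 2.6–4.0% | 83.2–83.8% | 838–850 | 6.70–6.66 |
| 0.4 | 4.7–7.2% | 84.0–85.0% | 856–879 | 6.63–6.54 |
| 0.5 | 7.4–11.1% | 85.0–86.5% | 881–918 | 6.54–6.40 |

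Example, R² = 11.1%: SE = 0.03466·√0.889 = 0.03268; power = Φ(3.060 − 1.96) = 86.4%, within rounding of the tabulated upper limit; 816/0.889 = 918.

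**4. Check on simulated trials.** 10,000 trials per value of r, 408 per arm, 50% v 60%, same three covariates. The Monte Carlo standard error of each power figure is about 0.4 points.

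| r | Chi-square | Adjusted | Gain (points) | Mean adjusted half-width (points) |
|---|---|---|---|---|
| 0 | 81.9% | 81.4% | −0.5 | 6.79 |
| 0.3 | 83.5% | 84.0% | 0.5 | 6.68 |
| 0.4 | 83.1% | 84.6% | 1.5 | 6.60 |
| 0.5 | 83.2% | 85.4% | 2.2 | 6.48 |

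The mean unadjusted half-width was 6.78 points. Type I error was 4.9–5.3% adjusted and 5.2–5.6% for the chi-square.

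**5. Which correlation is meant.** Here r is the correlation within each component. If r instead denotes the correlation of a baseline predictor with the yes/no outcome itself, then R² = r², and the pooled formula gives 83.5% power at r = 0.2, 85.4% at 0.3 and 91.3% at 0.5. The R² range of 2.6–11.1% corresponds to an outcome-level correlation of √0.026 = 0.16 to √0.111 = 0.33, so the two scales agree and the table uses the more cautious one.

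**The case against.** The best defence is that nothing is broken. Sample size and analysis use the same test on the same 10-point scale, power is met, and choosing a model over a matched, prespecified test is largely preference. **This stands**, and it is why the point is an improvement and not a correction.

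The gain is also small and rests on assumed correlations. The decision aid is meant to change knowledge between the two measurements, which may push the correlation down, and agreement in sign between attitude and intention is hard to predict from baseline scores. **This stands too.** The 0.5-point simulated gain at r = 0.3 is not clearly separated from simulation noise. The chi-square column shows that noise: its true power cannot depend on r, yet it ranges from 81.9% to 83.5% around an exact value of 82.7%. The steadier evidence is the R² and half-width results, which improve consistently as r rises.

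Two further objections concern the remedy. Changing the primary test changes what opens the participation hypothesis; this must be written down, but type I error stays near 5%. The attitude covariate needs a scoring direction, because the Appendix 3 items mix favourable and unfavourable poles; the endpoint needs the same rule, so adjustment adds no new requirement.

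Finally, calling the chi-square valid refers to the test under randomisation. The analysis set contains only women who answer at follow-up, and one-third early drop-out is allowed for. Possible attrition bias is a separate matter that adjustment does not settle.

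**Conclusion.** The point holds as a recommended improvement, not as an error. An unadjusted chi-square is the only primary analysis planned, although baseline values of all three endpoint components will be available for every randomised woman. With within-component correlations of 0.3–0.5, the loss is about 1–4 points of formula power (0.5–2.2 in simulated trials), or 22–102 women's worth of information, and about 0.1–0.4 points of confidence interval half-width. At zero correlation adjustment brings essentially no gain or loss. Confidence in the size is medium because the correlations and prevalences are assumed; the facts about the plan and the direction of the effect are not in doubt.

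**What to change.** In section 9.2, and to match in section 9.1.3:

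- Make the primary analysis a logistic regression of informed choice on arm, baseline knowledge score, baseline attitude score and baseline intention.
- Report the standardised (marginal) risk difference with its 95% confidence interval and p-value, naming the variance method (delta method or bootstrap). This keeps the absolute-difference scale of the sample size calculation.
- Keep the chi-square test as a supporting analysis.
- State that the adjusted test decides whether the participation non-inferiority hypothesis is examined.
- State that the baseline significance tests will not be used to decide on adjustment.
- Score baseline attitude by the same rule as follow-up attitude.

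Centre and baseline attitude–intention consistency are optional covariates. Adding consistency raised R² by at most 0.13 percentage points, and no material gain was shown for centre.

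The cost is SAP wording, a few lines of code and the variance step for the standardised risk difference. No extra data, sample size change or design change is needed.
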